4.2.5.3 Reasons for discontinuation of ATI and early study termination

The number and percentage of participants who discontinue ATI and who terminate from the study early will be tabulated by reason and treatment arm.

5 Study population

Participants for this trial will be recruited from among former HVTN 703/HPTN 081 (NCT02568215) study participants who met criteria for transition to Schedule 2 or Schedule 3 in that study and who meet the following inclusion/exclusion criteria.

Investigators should always use good clinical judgment in considering a volunteer's overall fitness for trial participation. Some volunteers may not be appropriate for enrollment even if they meet all inclusion/exclusion criteria. Medical, psychiatric, occupational, or other conditions may make evaluation of safety difficult, or may make volunteers unable to comply with the requirements of participation. For these reasons, some volunteers may be poor candidates for retention.

5.1 Inclusion criteria

1. **Estimated date of HIV-1 acquisition** within 8 weeks of (ie, before or after) having received an HVTN 703/HPTN 081 infusion (see HVTN 805/HPTN 093 SSP)
2. **Initiated ART within 28 weeks** of HVTN 703/HPTN 081 date of HIV-1 diagnosis
3. **Receiving continuous ART for at least 1 year**
 - ART interruptions of up to 7 days in duration and ≥ 90 days prior to enrollment are acceptable.
 - Within- and between-class changes in ART within the previous year are acceptable.
4. If on an NNRTI, **willingness and ability to switch** to a PI- or INSTI-containing regimen for at least 4 weeks prior to ART interruption
5. **Willingness to interrupt ART** for up to 24 weeks or up to the time of meeting ART re-initiation criteria (Section 3.3)
6. **Willingness to re-initiate ART** upon meeting study ART re-initiation criteria
7. **Willingness to use barrier protection** (ie, male or female condoms) for all sexual activity during the ATI and until confirmation of viral suppression following ART re-initiation
8. **Willingness for CRS staff to contact primary HIV care provider** to exchange information regarding HVTN 805/HPTN 093 and participant medical history

9. Site investigator anticipates that a **fully active alternative ART regimen** could be constructed and would be available in the event of virologic failure on the participant's current ART regimen.
10. **Access to a participating CRS** and willingness to adhere to study visit schedule and to be followed for the planned duration of the study
11. Ability and willingness to provide **informed consent**
12. **Assessment of understanding:** volunteer demonstrates understanding of this study; completes a questionnaire prior to enrollment with verbal demonstration of understanding of all questionnaire items answered incorrectly.
13. **Agrees not to enroll in another study** of an investigational research agent for the duration of the participant's trial participation

Laboratory Inclusion Values

Immunology/Virology

14. **HIV-1 infection**, with reactive HIV-1 antibody and any Multispot or Geenius HIV-1/HIV-2 results, documented by the HVTN 703/HPTN 081 HIV diagnostic algorithm
15. **Plasma HIV-1 RNA $\geq 1,000$ copies/mL** by any assay, prior to initiating ART
16. **CD4+ T-cell count ≥ 450 cells/mm³** obtained within 90 days prior to enrollment
17. One **plasma HIV-1 RNA below the lower limit of quantitation (LLOQ)** collected at each of the following:
 - at screening, within 90 days prior to enrollment; and
 - greater than 9 months prior to the screening HIV-1 RNA

Note: Sites must have results from locally available assays that are approved as standard-of-care by their regional governing bodies.

Hematology

18. **Hemoglobin (Hgb) ≥ 10.0 g/dL**
19. **Absolute neutrophil count (ANC) ≥ 750 cells/mm³**
20. **Platelets $\geq 100,000$ cells/mm³**

Chemistry

21. **Alanine aminotransferase (ALT)** < 2.5 times the institutional upper limit of normal and **direct bilirubin** within the institutional range of normal
22. **eGFR** > 60 mL/min/1.73m²

Reproductive Status

23. **Volunteers capable of becoming pregnant:** negative serum or urine beta human chorionic gonadotropin (β -HCG) pregnancy test performed at the screening visit and prior to enrollment. Persons who are NOT capable of becoming pregnant due to having reached menopause (no menses for 1 year) or having undergone total hysterectomy or bilateral oophorectomy or tubal ligation (verified by medical records) are not required to undergo pregnancy testing.
24. **Reproductive status:** A volunteer who is capable of becoming pregnant must agree to consistently use effective contraception (ie, IUD or hormonal; see [Appendix B](#) and HVTN 805/HPTN 093 SSP) for sexual activity that could lead to pregnancy from at least 21 days prior to enrollment through confirmation of viral suppression following ART re-initiation.
25. **Volunteers capable of becoming pregnant must also agree not to seek pregnancy through alternative methods**, such as artificial insemination or in vitro fertilization, until after confirmation of viral suppression following ART re-initiation.

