5.2 Exclusion criteria

1. Any **plasma HIV-1 RNA** \geq **LLOQ** (LLOQ: 75, 50, 40, or 20 copies/mL) within 12 months prior to enrollment
 - NOTE: Two “blips” (ie, plasma HIV-1 RNA > LLOQ) < 400 copies/mL are allowed if preceded and followed by values < LLOQ and if the blips occur more than 6 months prior to enrollment.

Note: Sites must have results from locally available assays that are approved as standard-of-care by their regional governing bodies.

2. **History of AIDS-defining illnesses** or US Centers for Disease Control (CDC) **Category C events** per the current list on the CDC website (see HVTN 805/HPTN 093 SSP)
3. **Autoimmune disease**, including Type I diabetes mellitus (Not excluded from participation: Volunteer with mild, stable and uncomplicated autoimmune disease that does not require consistent immunosuppressive medication and that, in the judgment of the site investigator, is likely not subject to exacerbation and likely not to complicate AE assessments).

4. **Immunosuppressive medications** received within 6 months before enrollment (Not exclusionary: [1] corticosteroid nasal spray; [2] inhaled corticosteroids; [3] topical corticosteroids for mild, uncomplicated dermatologic condition; or [4] a single course of oral/parenteral prednisone or equivalent at doses \leq 60 mg/day and length of therapy < 11 days with completion at least 30 days prior to enrollment)
5. **Blood products** received within 120 days before planned ART interruption
6. **Investigational research agents**, other than experimental vaccine(s) (See Exclusion Criterion #7), received within 30 days before planned ART interruption
7. **HIV or non-HIV experimental vaccine(s) received within the last 1 year.** Exceptions may be made by the HVTN 805/HPTN 093 Protocol Safety Review Team (PSRT) for vaccines that have subsequently undergone licensure by the FDA or by the national regulatory authority where the volunteer is enrolling. For volunteers who have received control/placebo in an experimental vaccine trial, the HVTN 805/HPTN 093 PSRT will determine eligibility on a case-by-case basis. For volunteers who have received an experimental vaccine(s) greater than 1 year ago, eligibility for enrollment will be determined by the HVTN 805/HPTN 093 PSRT on a case-by-case basis.

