6.1.2 Enrollment

- Participants undergoing an “ART switch” will be considered enrolled on the first day of the new ART medication.
- Participants who do not undergo an “ART switch” will be considered enrolled at the initiation of ATI (Day 0).

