6.1.3 ART Switch

ART switch

Participants taking NNRTI-based ART regimens are required to switch to a PI- or INSTI-based regimen at least 4 weeks before beginning ATI and must demonstrate viral suppression (ie, < LLOQ) on the new regimen before beginning ATI.

At the clinic visit initiating the ART switch, the participant will undergo the following procedures (see [Appendix E](#) and [Appendix H](#)):

- Targeted (ie, symptom directed) physical examination, including weight and vital signs
- Assessment of concomitant medications
- Intercurrent illness/adverse experiences (AEs)
- HIV transmission risk behavior assessment and counseling

- Contraception status assessment (for participants who are capable of becoming pregnant and who are sexually active in a way that could lead to pregnancy; see Section 6.6 and [Appendix B](#))
- Decision-making assessment
- Psychosocial assessment
- Blood collection for:
 - HIV PCR viral load
 - CD4+ and CD8+ T-cell counts
 - Hgb, ANC, platelets
 - ALT, direct bilirubin, eGFR
- Urine pregnancy test (persons not of reproductive potential due to having reached menopause (no menses for 1 year), or having undergone hysterectomy or bilateral oophorectomy or tubal ligation [verified by medical records], are not required to undergo pregnancy testing)

Post-ART switch contact

The site will make arrangements to contact the participant approximately 2 weeks after initiation of the new ART regimen to assess tolerability of the ART switch and willingness to continue. This contact may be conducted over the phone or in person; see HVTN 805/HPTN 093 SSP for details.

ATI qualification visit

Four weeks or more after initiation of the new ART regimen, participants undergoing an ART switch will return for a clinic visit during which they will undergo the following procedures (see [Appendix E](#) and [Appendix H](#)):

- Targeted (ie, symptom directed) physical examination, including weight and vital signs
- Assessment of concomitant medications
- Intercurrent illness/adverse experiences (AEs)
- HIV transmission risk behavior assessment and counseling
- Contraception status assessment (for participants who are sexually active in a way that could lead to pregnancy; see [Appendix B](#))

- Blood collection for:
 - HIV PCR viral load
 - CD4+ and CD8+ T-cell counts
 - Hgb, ANC, platelets
 - ALT, direct bilirubin, eGFR

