- Urine pregnancy test (persons not of reproductive potential due to having reached menopause (no menses for 1 year), or having undergone hysterectomy or bilateral oophorectomy or tubal ligation [verified by medical records], are not required to undergo pregnancy testing)

The procedures for the ATI qualification visit should be repeated as appropriate until viral suppression (ie, < LLOQ) is demonstrated. In general, ATI should be initiated approximately 2 weeks after the ATI qualification visit at which samples are collected that demonstrate viral suppression on the new ART regimen.

Any participant who is not virally suppressed at the ATI qualification visit will be retested on a weekly basis until virally suppressed. If not virally suppressed by approximately 12 weeks from the start of the ART switch, the participant should be referred to re-initiate their previous NNRTI-containing regimen, will not proceed to the ATI, and will be terminated from the study.

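### The 4-week NNRTI-free interval before ATI depends on current NNRTI use, so a volunteer switched by her own provider just before screening can start ATI 15 to 27 days after her last NNRTI dose

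*Protocol*

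**What the plan says.** Criterion 3 of Protocol Section 5.1 requires at least a year of continuous ART and adds: "Within- and between-class changes in ART within the previous year are acceptable". It sets no minimum time since such a change.

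Criterion 4 applies to a volunteer who is on an NNRTI. She must be willing and able to switch "to a PI- or INSTI-containing regimen for at least 4 weeks prior to ART interruption". Section 6.1.3 repeats the rule for the same people: "Participants taking NNRTI-based ART regimens are required to switch to a PI- or INSTI-based regimen at least 4 weeks before beginning ATI". It adds that they must "demonstrate viral suppression (ie, < LLOQ) on the new regimen before beginning ATI". The qualification specimens must come at least 28 days after the switch (Appendix E footnote 9). On timing, Section 6.1.3 says: "In general, ATI should be initiated approximately 2 weeks after the ATI qualification visit at which samples are collected that demonstrate viral suppression". Appendix H footnote 2 and Appendix K footnote 2 confine the switch phase to participants on NNRTIs.

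Everyone else goes from screening to Day 0. Appendix E footnote 15 asks that their screening specimens be at least 2 weeks old at Visit 4. Criterion 17 requires one HIV RNA below the LLOQ "at screening, within 90 days prior to enrollment; and" another more than 9 months before that one. Exclusion 1 bars any value at or above the LLOQ in the previous 12 months, apart from up to two low blips more than 6 months old. Non-switchers enrol on Day 0 (Section 6.1.2), so for them exclusion 1 runs up to that day.

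Section 2.4 gives prevention of resistant virus as the reason for the switch, and Section 10.1.1 singles out NNRTI users as a group of particular concern.

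**The concern.** The reason for the interval is recent NNRTI exposure, but the rule asks only whether the volunteer is on an NNRTI now. A woman whose provider changed her regimen last week has the same recent exposure as one who changes inside the study. She nevertheless meets neither the 4-week interval nor the 28-day viral load requirement.

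For other exposures, Section 5.2 does count time since receipt: 120 days for blood products, 30 days for investigational agents and live vaccines, and 14 days for other vaccines, all before planned ART interruption. No criterion sets a time since the last NNRTI dose, and no text explains the difference.

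What is at stake is individual safety. The protocol offers participants no direct health benefit (Section 10.2) and accepts that the risks of interruption must be minimized (Section 2.6). A protection it considers necessary for one route off NNRTIs should not lapse on another.

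**Working it through.** **Inputs**
- Required NNRTI-free interval for in-study switchers: 4 weeks = 28 days (criterion 4, Section 6.1.3).
- Switch to qualification sample: at least 28 days (Appendix E footnote 9).
- Qualification visit to ATI: about 14 days (Section 6.1.3).
- Appendix K, ART switch: target day -42, latest allowable day -29.
- Appendix K, ATI qualification: target day -14, earliest allowable day -28.
- Non-switchers, screening specimens to Day 0: at least 14 days (Appendix E footnote 15), at most 56 days (Appendix K).

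**The plan's own figure.** 28 + 14 = 42 days from switch to ATI, which reproduces the Appendix K target of day -42.

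**The outside-switch route.** Let x be the days from the provider's change to the screening specimens, and L the days from those specimens to ATI. The last NNRTI dose is taken to fall on the day of the change. NNRTI-free days at ATI = x + L, and the smallest L is 14.

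| x (days) | Earliest ATI, x + 14 | Short of 28 | Short of 29 |
|---|---|---|---|
| 1 | 15 | 13 | 14 |
| 7 | 21 | 7 | 8 |
| 13 | 27 | 1 | 2 |
| 14 | 28 | 0 | 1 |

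Against the 28-day rule, the gap therefore exists for changes 1 to 13 days before the specimens.

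**How narrow it is.** The interval is short only if x + L < 28. With x of at least 1, L must be 14 to 26 days. That is 26 - 14 + 1 = 13 of the 56 - 14 + 1 = 43 lead times Appendix K permits. This counts calendar days and is not a probability.

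**The viral load.** A change x days before screening puts the required suppressed sample x days into the new regimen. It falls short of the 28 days required of in-study switchers whenever x is 1 to 27. The sample is still drawn on the new regimen; it is only earlier.

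**Age of the last required sample at ATI.** For in-study switchers it is up to 14 days by Appendix E footnote 9, or up to 28 days by the Appendix K window. For non-switchers it is 14 to 56 days by the visit windows (criterion 17 alone would allow 90). That range applies to every non-switcher, including someone on an INSTI for years, so it is not part of this gap.

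**Scale.** The documents give no count of such volunteers. One participant would be 1/61 = 1.6% of the largest planned sample or 1/16 = 6.3% of the smallest.

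**The case against.** The strongest case against is that no harm is shown and several safeguards remain.

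- **Monitoring.** Viral load is checked weekly to week 8 and every 2 weeks to week 24 of Schedule 1. The meta-analysis described in Section 2.4 found new resistance mutations in 0% (95% CI 0% to 1%) with monitoring at least every 2 weeks, against 9% (3% to 16%) with less frequent monitoring. This is the most relevant counter-evidence and it stands. It is not specific to NNRTIs, because the prior regimens were not known for all the trials.
- **Risk.** Section 10.1.1 calls the resistance risk theoretical. The documents mention long NNRTI half-lives but give no clearance time, so whether 15 days rather than 28 matters cannot be settled from them.
- **Wording.** Being on an NNRTI has no reference date in criterion 4, and screening may run over several contacts. A volunteer still on an NNRTI at her first contact could fairly be treated as covered. This narrows the gap but does not remove it for someone changed before first contact.
- **Site discretion and later checks.** Medication review, provider contact (criterion 8), an available active alternative regimen (criterion 9), investigator judgment and PSRT review all apply, but none sets an interval. ARV-detection samples begin at ATI week 4 and their testing is discretionary. Resistance testing follows poor re-suppression. Both come too late to prevent anything.
- **The SSP.** The 14-day minimum is worded as advice and refers to the SSP, which may contain a rule. That would help, but the eligibility text should still agree with it.

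A reader might infer that these volunteers start ATI with no viral load check on the new regimen. The documents do not support that: criterion 17 requires a suppressed screening sample, and exclusion 1 bars any known value at or above the LLOQ up to Day 0, apart from the allowed older blips.

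**Conclusion.** The point holds as a minor gap in the eligibility rules. Followed as written, the protocol lets a recent outside switcher start ATI 15 to 27 days after her last NNRTI dose, 1 to 13 days short of its own 28-day rule, and without a suppressed sample after at least 4 weeks on the new regimen.

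This rests on three assumptions: the change falls 1 to 13 days before the screening specimens, ATI begins at the 14-day minimum, and the SSP adds nothing. The gap shrinks as the lead to ATI grows and is gone by a lead of 27 days.

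Two further inferences would go too far. One is that NNRTI persists at 15 days and would select resistance; no document gives the pharmacology for that. The other is that the comparison of VRC01 with placebo, or the time-to-re-initiation endpoint, is distorted. Few participants are likely to be affected and nothing ties such changes to parent-trial arm, so no group-level effect is claimed. Confidence is medium, mainly because the SSP was not available.

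**What to change.** - Reword criterion 4 and Section 6.1.3 to cover volunteers who are on an NNRTI at screening or took one within 4 weeks before their screening specimens.
- Whoever made the change, require at least 4 weeks since the last NNRTI dose before ART interruption, and one HIV RNA below the LLOQ drawn at least 4 weeks after the change.
- Match the footnotes: Appendix E footnotes 8 and 15, Appendix H footnote 2, and Appendix K footnotes 2 and 3.

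The cost is a short text change, some waiting and possibly one repeat viral load for a few volunteers. Under the fix, ATI would come 28 days after the change at the earliest, or 42 days with the usual 2-week wait after the qualifying sample. Compared with the earliest date now possible, the delay is:
- change 1 day before screening: 28 - 15 = 13 to 42 - 15 = 27 days;
- change 13 days before: 28 - 27 = 1 to 42 - 27 = 15 days;
- change 27 days before (earliest ATI now 27 + 14 = 41): 0 to 42 - 41 = 1 day.

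The longest delay is therefore just under 4 weeks.

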5.2 Exclusion criteria

1. Any **plasma HIV-1 RNA** \geq **LLOQ** (LLOQ: 75, 50, 40, or 20 copies/mL) within 12 months prior to enrollment
 - NOTE: Two “blips” (ie, plasma HIV-1 RNA > LLOQ) < 400 copies/mL are allowed if preceded and followed by values < LLOQ and if the blips occur more than 6 months prior to enrollment.

Note: Sites must have results from locally available assays that are approved as standard-of-care by their regional governing bodies.

2. **History of AIDS-defining illnesses** or US Centers for Disease Control (CDC) **Category C events** per the current list on the CDC website (see HVTN 805/HPTN 093 SSP)
3. **Autoimmune disease**, including Type I diabetes mellitus (Not excluded from participation: Volunteer with mild, stable and uncomplicated autoimmune disease that does not require consistent immunosuppressive medication and that, in the judgment of the site investigator, is likely not subject to exacerbation and likely not to complicate AE assessments).

4. **Immunosuppressive medications** received within 6 months before enrollment (Not exclusionary: [1] corticosteroid nasal spray; [2] inhaled corticosteroids; [3] topical corticosteroids for mild, uncomplicated dermatologic condition; or [4] a single course of oral/parenteral prednisone or equivalent at doses \leq 60 mg/day and length of therapy < 11 days with completion at least 30 days prior to enrollment)
5. **Blood products** received within 120 days before planned ART interruption
6. **Investigational research agents**, other than experimental vaccine(s) (See Exclusion Criterion #7), received within 30 days before planned ART interruption
7. **HIV or non-HIV experimental vaccine(s) received within the last 1 year.** Exceptions may be made by the HVTN 805/HPTN 093 Protocol Safety Review Team (PSRT) for vaccines that have subsequently undergone licensure by the FDA or by the national regulatory authority where the volunteer is enrolling. For volunteers who have received control/placebo in an experimental vaccine trial, the HVTN 805/HPTN 093 PSRT will determine eligibility on a case-by-case basis. For volunteers who have received an experimental vaccine(s) greater than 1 year ago, eligibility for enrollment will be determined by the HVTN 805/HPTN 093 PSRT on a case-by-case basis.
8. **Licensed live attenuated vaccines** received within 30 days before planned ART interruption (eg, measles, mumps, and rubella [MMR]; oral polio vaccine [OPV]; varicella; yellow fever; live attenuated influenza vaccine)
9. **Licensed vaccines that are not live attenuated vaccines** received within 14 days before planned ART interruption (eg, tetanus, pneumococcal, hepatitis A or B, influenza)
10. **Significant unstable cardiac or cerebrovascular disease** (eg, angina, congestive heart failure [CHF], recent cerebrovascular accident [CVA], or myocardial infarction [MI])
11. **Positive Hepatitis B surface antigen (HBsAg) or positive HCV RNA** (Not exclusionary: positive HCV Ab with negative HCV RNA)
12. **Pregnant or breastfeeding**
13. **Clinically significant medical condition**, physical examination findings, clinically significant abnormal laboratory results, or past medical history with clinically significant implications for current health. A clinically significant condition or process includes but is not limited to:
 - A process that would affect the immune response;
 - A process that would require medication that affects the immune response;

- Any contraindication to repeated blood draws, including inability to establish venous access;
 - A condition that requires active medical intervention or monitoring to avert grave danger to the volunteer's health or well-being during the study period; or
 - Any condition specifically mentioned among the exclusion criteria.
14. **Any medical, psychiatric, occupational, or other condition** that, in the judgment of the investigator, would interfere with, or serve as a contraindication to, protocol adherence, assessment of safety, or a volunteer's ability to give informed consent
 15. **Any medical, psychiatric, occupational, or other condition** that, in the judgment of the investigator, could be exacerbated by events associated with protocol participation, which include: ATI, low-level viremia, subsequent viral rebound, and ART re-initiation
 16. **HIV dementia or other neurologic disease** that, in the judgment of the investigator, would be a contraindication to study participation
 17. **Psychiatric condition that precludes compliance with the protocol.** Specifically excluded are persons with psychoses within the past 3 years, ongoing risk for suicide, or history of suicide attempt or gesture within the past 3 years.
 18. **Malignancy** (Not excluded from participation: Volunteer who has had malignancy excised surgically and who, in the investigator's judgment, has a reasonable assurance of sustained cure, or who is unlikely to experience recurrence of malignancy during the period of the study)
 19. **Current untreated or incompletely treated active tuberculosis disease or current latent tuberculosis infection** (Not excluded from participation: Volunteer who has latent tuberculosis infection and is undergoing treatment, with at least one month of treatment completed)
 20. **Untreated or incompletely treated syphilis, gonorrhea, or chlamydia infection**

